We will be purchasing the device from the manufacturer's website. We will be purchasing the devices via funds awarded by the James E. Eckenhoff Residents' Research Award.

The device will be stored in the PI's key-locked office, until it is given to a research team member to be given to a subject after recruitment and prior to their procedure. Research personnel will bring the appliance to the preoperative holding area & will help mold it for the patient, and will insert it prior to transport to the operating suite. The device will remain in place until the completion of procedure, unless the anesthesia provider in the room feels it needs to be removed for any reason. The patient or anesthesia personnel can remove the device at their leisure after completion of the procedure.

PROCEDURES INVOLVED:

The study participants will be recruited into two groups: patients wearing an anti-snoring appliance device during an anesthetic sedation procedure; and those who do not wear an anti-snoring device. To ensure anesthetic providers have easy access to the patient's airway for standard of care manipulation (if needed), the patients eligible for this study would be those who are undergoing procedures below the umbilicus (e.g. gynecological, urological, orthopedic, etc.) in addition to having a STOP-BANG score of 2 or greater. This will ensure patient safety and provide a wide demographic of potential subjects to increase the generalizability of the study.

For both patient groups, the study procedure is the same. Eligible patients will be identified by chart review of various elements of the electronic medical record, as follows:

Patients will be identified and be seen by the study team in the pre-operative clinic on 17th floor Lavin and in the holding area to interview individuals who are to undergo eligible anesthetic sedation procedures as above. If the patient agrees to participate in the study, they will be randomized at that time to one of the two groups (anti-snoring appliance device to be used for procedure or not).

The groups in the prospective, randomized, controlled trial in patients undergoing anesthetic sedation procedures will be as follows:

Group #1: Anti-snoring appliance (Zyppah) that will be utilized during their procedure
Group #2: Control group, that will not utilize anti-snoring appliance

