Individual subjects and anesthetic providers will participate in the study for the duration of their procedure requiring anesthetic sedation. It will take approximately 3 months to enroll participants and approximately 3 months to perform data analysis.

INCLUSION AND EXCLUSION CRITERIA

Inclusion criteria

Adult patients (age 18-89 years old)

Undergoing procedures below the umbilicus requiring anesthetic sedation without an invasive airway

STOP-BANG score of 2 or greater.

English or Spanish language speaking

Exclusion criteria

Patients requiring general anesthesia.

Sleep apnea

Serious breathing or respiratory disorders such as COPD, asthma, emphysema

Poor dental health including severe gum disease, loose teeth, abscess, mouth sores, bleeding gums

Dental implant place within last 3 months

TMJ disorder

Mouth or jaw pain

Full dentures

Wear braces

Sleep with CPAP or other devices

Other special populations (individuals who are not yet adults, prisoners, vulnerable populations, pregnant) will also be excluded.

VULNERABLE POPULATIONS:

Will not be a part of study.

PARTICIPANT POPULATION(S)

Accrual Number:	Category/Group: (Adults/Children Special/Vulnerable Populations)	Consented: Maximum Number to be Consented or Reviewed/Collected/Screened	Enrolled: Number to Complete the Study or Needed to Address the Research Question
Local	Adults	28	28
Study-wide		28	24
Total:		28	24

RECRUITMENT METHODS

Patients undergoing an eligible procedure requiring anesthetic sedation will be identified by the anesthesiology team by chart review and the schedule in the pre-operative clinic on the 17th floor Lavin pavilion prior to their procedure. They may also be approached by the research team the morning of their procedure for possible enrollment into the study. If the potential subject is interested in the study a study team member will ask for the subject's email address to send an Econsent using REDCap for their review.

The source of participants will be NMH pavilions (Galter, Feinberg, Lavin) in addition to Prentice Women's Hospital.

COMPENSATION FOR PARTICIPATION IN RESEARCH ACTIVITIES

There will be no compensation for participation; however, patients who are randomized into one of the anti-snoring device groups will be allowed to keep the device, if they wish.

WITHDRAWAL OF PARTICIPANTS

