We utilized a study by Qiansong Xiao et al titled “Comparison of Nasopharyngeal Airway Device and Nasal Oxygen Tube in Obese Patients Undergoing Intravenous Anesthesia for Gastroscopy: A Prospective and Randomized Study”, which compared the oxygen saturation levels in patients who did or did not have an invasive nasopharyngeal airway at the beginning of the anesthetic sedation procedure, to perform our power analysis. 260 patients were included and randomized; with 3 patients excluded due to failure of the nasopharyngeal airway. Based on the differences in “change in SpO₂” and “raising the mandible” between their test and control groups, and power analysis was completed with an alpha value of 0.05 and power value of 80%. The n per group that was calculated to provide the appropriate power to identify a statistical difference was 12 patients per study group. To compensate for patients in our study being less obese we increased the number per group to 14 subjects. We plan to approach 28 subjects and randomize 28 patients to 2 groups, allowing for patients who may not end up getting their procedure or instances where data collection is incomplete or absent.

Statistical analysis: Data will be compared between all groups using paired t-test with p< 0.05 required to reject the null hypothesis.

Data Security:

All collected data will be stored in REDcap using NM password protected computers for data entry. Data in REDcap is backed up nightly using NM servers which are only accessible to the NM IT administrator. Paper documents generated during the study will be stored in Arkes Pavilion 10th floor Department of Anesthesiology locked research cabinet. Data both paper and electronic will be destroyed 5 years after the completion of the study using current department policy and approved vendors.

PROVISIONS TO MONITOR THE DATA TO ENSURE THE SAFETY OF PARTICIPANTS N/A

PROVISIONS TO PROTECT THE PRIVACY INTERESTS OF PARTICIPANTS

Patients in this study undergoing a procedure under anesthetic sedation can be stressful. If a subject does not feel comfortable with participating, they will have the option to opt out at any time and it will not impact their care if they choose to do so.

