Research staff will interact with anesthesia providers on two occasions (at the beginning for ~10 minutes in the pre-operative area and end of procedure for ~5 minutes in the post-operative care area), staff will interact with participants for ~30 minutes prior to the procedure in the pre-operative area in addition to helping mold the mouthpiece.

COMPENSATION FOR RESEARCH-RELATED INJURY

n/a

ECONOMIC BURDEN TO PARTICIPANTS

There is no cost to the patient to be in this study. The device is being paid for by the Department of Anesthesiology.

CONSENT PROCESS

Introduction of the study to the potential participant and consent will take place in Northwestern Hospital's Lavin Anesthesia Pre-Operative Clinic. The potential participant will then be sent a consent document from REDcap which includes the electronic consent document for their review. If the potential participant consents one of the study team members will contact them to discuss the day of surgery plan. The participant will receive instructions on acquisition and preparation of the device, in addition to instructions on bringing it to the day of their procedure. REDcap electronic consent will be utilized to decrease the number of times the paper consent would be touched. Multiple times throughout the process, the participant will be reminded that this in no way affects their standard of care and that participation can be withdrawn at any time.

NON-ENGLISH SPEAKING PARTICIPANTS

While we do not anticipate non-English speaking participants on this study, if a non-English speaking patient would benefit from enrollment in this study, the investigator will adhere to the IRB's standard requirements for non-English speaking participants.

This includes providing the IRB the following in a timely fashion:

- Certified translations of all documents the participant will be required to complete (such as surveys and questionnaires);
- A qualified translation service will be used to translate patient facing documents and consent forms
- Certified translations of the modified consent document in a language understandable to the non-English speaking participant if the English version of the approved consent document undergoes subsequent modification;

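### Patients who agree in the pre-operative clinic are randomised before the day of surgery, so allocations can go to patients who never have the procedure and have no primary outcome

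*Combined protocol and SAP*

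**What the plan says.** - **Time of allocation.** Procedures Involved: "If the patient agrees to participate in the study, they will be randomized at that time to one of the two groups".
- **Place of contact.** The same section gives two places: "Patients will be identified and be seen by the study team in the pre-operative clinic on 17th floor Lavin and in the holding area". Recruitment Methods adds a same-day route: "They may also be approached by the research team the morning of their procedure for possible enrollment into the study". Consent Process names one place only: "consent will take place in Northwestern Hospital's Lavin Anesthesia Pre-Operative Clinic". It then has a team member contact the consented patient about arrangements for surgery, so on this route consent comes before the day itself.
- **Expected losses.** Data Statistics randomises 28 patients to two groups, "allowing for patients who may not end up getting their procedure or instances where data collection is incomplete or absent". It gives no rate. The study-wide row of the accrual table has 24 completing; the local row has 28.
- **Margin.** The power analysis gave 12 per group. The rise to 14 is explained by this trial's patients being less obese than those in the source study.
- **Anesthetic and arm.** The exclusion criteria list "Patients requiring general anesthesia". Anesthesia providers are not blinded. The data of withdrawn patients are deleted. No analysis population is defined.
- **Device.** Study Intervention(s): "Research personnel will bring the appliance to the preoperative holding area", where they help mould and insert it. Consent Process: "The participant will receive instructions on acquisition and preparation of the device", together with instructions to bring it on the day.

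**The concern.** The primary endpoint is a count of airway interventions during a sedation case. A patient who is randomised and then has no such case contributes nothing to it. Every day between allocation and sedation leaves room for the procedure to be cancelled, the anesthetic plan to change or the patient to withdraw. In a trial of 14 per arm, a few such losses use up the whole margin.

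Two different harms need separating. A cancellation unrelated to the arm costs precision and wastes an allocation, but does not bias the comparison. A departure that depends on the arm can bias it. The plausible routes are a patient who has been told the arm and withdraws, and a change of anesthetic plan by someone who knows the arm. The plan has no rule for either case, beyond deleting the data of those who withdraw.

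Allocation before the day of surgery also appears unnecessary under Study Intervention(s), since the device is brought, moulded and inserted by research staff on site.

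**Working it through.** **The plan's own figures.** The 12 per group cannot be reproduced, because no difference, standard deviation or event rates are given. The accrual table implies a tolerated loss of (28 − 24)/28 = 14.3%, or 2 per arm if evenly spread.

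**Chance that an arm falls below 12.** Inputs: 14 per arm and 12 needed (Data Statistics). The loss rate q is not in the documents; I assume 5%, 10% or 15%, with independent losses. An arm falls below 12 when it loses 3 or more of 14:

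p = 1 − [(1−q)^14 + 14q(1−q)^13 + 91q²(1−q)^12]; either arm: 1 − (1−p)².

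*All 28 randomised in clinic:*
- q = 5%: p = 1 − (0.488 + 0.359 + 0.123) = 3.0%; either arm 5.9%.
- q = 10%: p = 1 − (0.229 + 0.356 + 0.257) = 15.8%; either arm 29.2%.
- q = 15%: p = 1 − (0.103 + 0.254 + 0.291) = 35.2%; either arm 58.0%.

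*Half enrolled on the morning with no such loss.* If each patient is equally likely to come by either route, the rate per patient halves to 2.5%, 5% or 7.5%. Then p = 0.5%, 3.0% or 8.2%, and the either-arm figure is 0.9%, 5.9% or 15.8%.

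**What falling below 12 costs.** If 12 per group gives 80% power in a two-sided two-sample t-test at 0.05, the implied standardised difference is 1.197 (back-solved, so an assumption). On that basis:

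| Patients analysed | Power |
|---|---|
| 14 and 14 | 86.2% |
| 12 and 12 | 80.0% |
| 13 and 11 | 79.7% |
| 11 and 11 | 76.1% |

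Twelve is therefore not a cliff; power declines gradually.

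**The margin is used twice.** The 2 extra patients per group are justified by lower obesity and then also asked to cover losses. If 14 are needed for the first reason, cover for losses needs 14/(1−q): 14/0.95 = 14.7, 14/0.90 = 15.6, 14/0.85 = 16.5, that is 15, 16 or 17 per group.

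**Illustration of arm-dependent loss.** With a normal outcome, losing the 2 patients who would have had the highest counts from one arm of 14 lowers that arm's mean by about 0.24 SD. This is an extreme case, not a forecast.

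**Which section governs the device.** If staff supply and mould it in the holding area, nothing requires earlier allocation. If participants obtain it and bring it, allocation must come before the day. The two sections cannot both hold.

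**The case against.** Three stronger readings are tempting, and the documents do not support them.

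- *Everyone is randomised in the clinic.* A reader of Consent Process alone would infer this. Procedures Involved also names the holding area, and Recruitment Methods allows an approach on the morning. For those patients, randomising at agreement is already close to the fix. The share recruited in clinic is not stated, so the 6%, 29% and 58% are an upper case.
- *Cancellations are made with the arm known.* Providers are unblinded, but staff are described as meeting them in the pre-operative area at the start. Nothing shows that the case provider, or whoever cancels a case, knows the arm before the day of surgery.
- *A change of anesthetic means exclusion.* The general anesthesia criterion points that way before a case starts, but no text drops a randomised patient whose plan changes. Requested and documented anesthesia type are both collected, and conversion to general anesthesia is kept as an adverse event.

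It is also fair to say that the loss rates are assumed, that a fall to 11 in one arm costs little power, and that later allocation leaves other losses in place. All of this stands and limits the size of the point. It does not remove it: the clinic route exists, the plan expects randomised patients without a procedure, and it does not say how they are handled.

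**Conclusion.** The point holds in a limited form and should be dealt with before enrolment. Clinic-route patients can be lost between allocation and sedation, and the plan anticipates this. The main cost is wasted allocations against a margin already committed to another purpose. Bias is a possibility, confined to withdrawals and changes of plan made with knowledge of the arm; its size cannot be derived from the documents.

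The chance that at least one arm ends below 12 ranges from about 1% (half enrolled that morning, 5% loss among clinic patients) to 58% (all randomised in clinic, 15% loss). Both the loss rate and the split between routes are assumptions. The figures also take 14 per arm as planned and independent losses.

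**What to change.** 1. Keep consent in the clinic. Change Procedures Involved so that every patient is randomised in the holding area on the day of the procedure, after eligibility and the plan for sedation are confirmed and immediately before the device would be moulded.
2. Make Procedures Involved, Recruitment Methods and Consent Process agree on where patients are enrolled.
3. Reconcile Study Intervention(s) with Consent Process on who supplies the device. Allocation on the day works only with the study-supplied device described under Study Intervention(s).
4. State that all patients randomised at that point are analysed in their allocated arm, and report any losses by arm and reason.

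The cost is a change of wording and one more step on the morning of the procedure, when research staff are already due in the holding area with the device. Losses before the procedure would then mostly fall before allocation and could be replaced. Later randomisation does not prevent conversion to general anesthesia during the case, later withdrawal or incomplete data, so the fourth item is needed whatever the timing.

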Participants will be randomized to treatment groups based on a random computer-generated (<https://www.randomizer.org>). Anesthesia providers will not be blinded to randomization, and research personnel will observe the procedure to collect all outcome measures in this study.

For group 1, the study team will aid them in molding and preparing the device in the pre-operative area. Anesthesia providers will be instructed on how the device works and when to place it (with aid from the research team) in addition to receiving a question and answer sheet and protocol they can follow to take with them to the operating room. Prior to the administration of anesthetic medications, the patient will be aided in inserting the device, and wear it throughout the entirety of the case. Regardless of the group, from the start of sedation until the patient leaves the procedure suite. When an anesthesia provider believes they make a clinically significant airway intervention (either via jaw lift, head turning, etc.) they will be instructed to use the “mark now” icon in the anesthetic record and utilize the free text to indicate what intervention was done and why.

All standard practices and standard monitors for anesthetic sedation cases will be utilized.

A post-survey will be administered to anesthesia providers in group 1 to gauge satisfaction.

Anesthetic record will be reviewed by research team members following the end of the case.

DATA AND SPECIMEN BANKING

We will collect data including reason for procedure, type of procedure, and patient demographics (including medical history, sex, age, and weight); in addition to data collected via electronic chart review including: Documented Obstructive Sleep Apnea (OSA), date of procedure, surgical case length, anesthesia type requested, anesthesia type documented, Provider team staff composition, documented neuraxial or nerve block procedure (if applicable), “in room” time, max/min heart rate, min/max oxygen saturation, number of instance oxygen saturation fell below 92%, % of time during case where oxygen saturation was below 92%, min/max end tidal CO₂, min/max blood pressure, total dose of hypnotic & narcotic given, “out of room” time, adverse events noted in charting, free-text written by providers, and total hospital length of stay.

SHARING RESULTS WITH PARTICIPANTS

Results will not be shared with participants.

STUDY TIMELINES

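### Randomisation uses a public website generator with no stated ratio, sequence type, sequence holder, log or concealment, so foreknowledge or redraws cannot be excluded and 14 per group is not guaranteed

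*Combined protocol and SAP*

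**What the plan says.** All references are to the combined protocol and SAP.

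- **Method** (PROCEDURES INVOLVED): "Participants will be randomized to treatment groups based on a random computer-generated", then a website address. As the text reads, the sentence has no noun after its last adjective, so it does not say whether a list is made in advance or each assignment is drawn live.
- **Timing** (same section): "If the patient agrees to participate in the study, they will be randomized at that time to one of the two groups".
- **Who meets patients** (same section): "Patients will be identified and be seen by the study team in the pre-operative clinic". The study team also helps mould the device. Nobody is named as generating, holding or releasing assignments.
- **Blinding and outcome collection** (same section): "Anesthesia providers will not be blinded to randomization, and research personnel will observe the procedure to collect all outcome measures in this study". An intervention is marked in the anesthetic record "When an anesthesia provider believes they make a clinically significant airway intervention".
- **Numbers** (DATA MANAGEMENT AND CONFIDENTIALITY, Data Statistics): 12 per group calculated, raised to 14, and "We plan to approach 28 subjects and randomize 28 patients to 2 groups". A 1:1 ratio is implied by this and stated nowhere.
- **Systems** (Data Security): "All collected data will be stored in REDcap". REDCap is also used for electronic consent (RECRUITMENT METHODS, CONSENT PROCESS). It is not mentioned for allocation.
- **Team** (QUALIFICATIONS TO CONDUCT RESEARCH AND RESOURCES AVAILABLE): the PI, two residents and one research assistant.

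**The concern.** The method sentence can be read in two ways, and each leaves something open.

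- **A list made in advance.** Nothing says who keeps it or that recruiters cannot see it. Someone who knew the next arm could decide whom to approach, and when, by expected airway difficulty. Patients are found by chart review and STOP-BANG is an entry criterion, so that difficulty is partly visible beforehand.
- **A live draw for each patient.** The next arm cannot then be foreseen, but no log or independent holder is described. An unwelcome result could be redrawn without trace, and nothing would fix the arm sizes. Because WITHDRAWAL OF PARTICIPANTS has withdrawn patients' data deleted, the final dataset alone could not account for every assignment made.

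The link to consent is also loose. CONSENT PROCESS describes an introduction in clinic and then an electronic form sent for review. If agreeing means verbal interest, the arm could be known before consent is documented.

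With 28 patients, steering a few could move the comparison. Selection on unrecorded clinical impressions cannot be reliably repaired in analysis. A secondary consequence is that the planned 14 per group may not be reached.

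**Working it through.** **1. The plan's own figure.** 2 × 14 = 28 reproduces. The 12 per group does not, because no effect size, standard deviation or event rates are given.

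**2. What is specified.**

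| Element | In the documents |
|---|---|
| Source of randomness | Public website generator |
| Ratio | Not stated; 1:1 implied by 14 per group |
| Sequence type, blocking | Not stated |
| Who generates, holds, releases | Not stated |
| Concealment, log | Not stated |
| Point of assignment | When the patient agrees; no link to recorded consent |

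**3. Arm sizes under simple 1:1 randomisation (an assumption).** Let X, the size of one arm, be Binomial(28, 0.5).

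- P(14/14) = C(28,14)/2^28 = 40,116,600/268,435,456 = 0.149.
- P(smaller arm below 14) = 1 − 0.149 = 0.851.
- P(smaller arm below 12) = P(X ≤ 11) + P(X ≥ 17) = 0.345.
- P(smaller arm 8 or fewer) = 0.036.

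**4. What imbalance costs in power.** The effect size must be assumed. I back-solved the standardised difference d that gives 80% power with 12 per group in a two-sample t-test, two-sided alpha 0.05: d = 1.197. The plan does not state sidedness and names a paired t-test; I used the two-sample form because the arms hold different patients. The noncentrality is d × √(n1 × n2/(n1 + n2)), with 26 degrees of freedom for every split of 28.

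| Split | Noncentrality | Power |
|---|---|---|
| 14/14 | 1.197 × √7 = 3.17 | 0.862 |
| 11/17 | 1.197 × √(187/28) = 3.09 | 0.845 |
| 10/18 | 1.197 × √(180/28) = 3.03 | 0.832 |
| 9/19 | 1.197 × √(171/28) = 2.96 | 0.812 |
| 8/20 | 1.197 × √(160/28) = 2.86 | 0.786 |

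Weighting each split by its binomial probability gives an average power of 0.848. The cost is 0.862 − 0.848 = 0.014, about 1.4 percentage points. Power falls below 80% only at 8/20 or worse, which has probability 0.036.

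**5. What blocking costs in predictability.** Suppose recruiters know that blocks of 4 are used and see past assignments. The fourth place is always certain, and the third is certain when the first two match (probability 1/3).

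- Certain assignments: (1 + 1/3)/4 = 33%.
- Best-guess accuracy: (1/2 + 2/3 + 2/3 + 1)/4 = 71%.

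For a single 14/14 list, simulation gives about 7% and 60%. For an unseen simple sequence the figures are 0% and 50%. Blocks of 4 would secure 14/14 (28/4 = 7 blocks), but without concealment they make foreknowledge easier.

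**The case against.** The strongest reply is that the documents are silent, and silence is not a flaw in conduct. A reader might infer that recruiters work from an open list and can know the next arm before enrolling a patient. The text does not support that: no list is described, agreement is placed before randomisation, and a live draw cannot be foreseen. The person holding the assignments is not named, so overlap with recruiting is an inference from the small team. A public generator is not a defect in itself, and it could be used to make a balanced list. All of this stands, and it limits the point to what cannot be excluded.

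A reader might also take the 34.5% chance of an arm below 12 to mean that a third of such trials would be underpowered. That does not follow. The other arm grows as one shrinks, and at the back-solved effect power stays above 80% down to 9/19. The 34.5% also rests on simple randomisation, which the plan does not state; a target of 14 per group fits a balanced list at least as well.

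Finally, unblinded providers judging the endpoint is a separate problem of performance and detection. Concealment does not cure it. It is relevant here only because the trial has no blinding to fall back on.

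What remains is that no safeguard is specified under either reading of the method.

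**Conclusion.** The point holds as a gap in the allocation procedure that should be closed before enrolment. Ratio, sequence type, independent holder, log and concealment are all absent, and release of the assignment is not tied to recorded consent. Foreknowledge and unlogged redraws therefore cannot be excluded. The documents do not show either, and the size of any resulting selection bias cannot be derived from them.

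Fourteen per group is not guaranteed, but this is the lesser part. Under simple 1:1 randomisation the exact split occurs in 14.9% of trials, at an average power cost of about 1.4 points. That cost rests on the back-solved d of 1.197, a two-sided 5% test and no losses. Concealment is the substance and blocking is secondary.

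**What to change.** Replace the website draw with text along these lines:

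> Allocation is 1:1. The sequence is prepared by a member of the study team who does not enrol patients and is not accessible to those who do. Each assignment is released only after consent and eligibility have been recorded, and every release is logged with date and time. Release is through the REDCap randomisation module or, if that is not available, through sequentially numbered, opaque, sealed envelopes.

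Blocking is optional. If it is used to secure 14 per group, vary the block sizes, do not disclose them to recruiters, and keep them out of any document that recruiters see.

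The cost is a short set-up in a system the trial already uses for consent and data, if the module is available (the documents do not say), or a set of envelopes. One person in a team of four is kept out of enrolment. With blocking, the small downside is that some assignments late in a block may still be guessed. The change must be in place before the first patient, because concealment cannot be added afterwards.

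### Study papers for the operating room are described for device-arm providers with no counterpart for control providers, around an unblinded, judgement-based primary count

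*Combined protocol and SAP*

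**What the plan says.** All of the relevant text on procedure is under PROCEDURES INVOLVED, in this order.

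- Blinding and data collection: "Anesthesia providers will not be blinded to randomization, and research personnel will observe the procedure to collect all outcome measures in this study".
- The next paragraph opens with the device arm: "For group 1, the study team will aid them in molding and preparing the device in the pre-operative area".
- The sentence after that names no group: "Anesthesia providers will be instructed on how the device works and when to place it (with aid from the research team"), and it continues "in addition to receiving a question and answer sheet and protocol they can follow to take with them to the operating room".
- After a sentence on inserting the device before anesthetic drugs are given, the scope widens in a sentence fragment: "Regardless of the group, from the start of sedation until the patient leaves the procedure suite".
- The marking rule follows. Its trigger is "When an anesthesia provider believes they make a clinically significant airway intervention", and the provider then uses the mark-now "icon in the anesthetic record and utilize the free text to indicate what intervention was done and why".
- The satisfaction survey of providers is expressly limited to group 1.

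STUDY ENDPOINTS defines the primary endpoint as the total number of airway interventions in a case and lists the manual manoeuvres included. The closing paragraph under PROVISIONS TO PROTECT THE PRIVACY INTERESTS OF PARTICIPANTS gives two staff contacts with providers, about 10 minutes before and 5 minutes after the case, and does not limit them to an arm.

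**The concern.** The provider performs the manoeuvres, decides when one is needed, and decides whether it was significant enough to mark. If providers in one arm have study papers in hand and those in the other do not, the arms may differ in more than the device.

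Two routes are possible, and they can pull in opposite directions. A document in the room may remind the provider to mark, which makes the device-arm count more complete and hides a benefit. Material about how the device functions may raise expectation, so that the provider intervenes or marks less, which produces an apparent benefit. Once the data are collected, neither can be separated from a device effect.

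**Working it through.** **Step 1. Who gets the papers.** The sentence on the briefing and papers names no group. It stands between the opening reference to group 1 and the later widening to both groups, and a briefing on placing a device has no use in a control case. The natural reading is group 1. No sheet or carried protocol for control providers is described anywhere.

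**Step 2. What the papers contain.** The only content described is use and placement of the device. Nothing says that they define an airway intervention, state when to intervene, or explain marking.

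**Step 3. What is common to both arms.** The marking rule follows the widening of scope and has no group limit. Observation by research personnel is not limited by group either.

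**Step 4. Which record supplies the primary count.** Observers are to collect all outcome measures. Providers also mark interventions, and the anesthetic record is reviewed after the case. The plan does not say which record supplies the count. The marking trigger also adds a threshold of clinical significance that the endpoint definition does not contain.

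**Step 5. The plan's own figure.** The point disputes no number. The 12 per group under Data Statistics cannot be reproduced, because no effect size, SD or rates are given. Solved backwards at two-sided 0.05 and 80% power (normal approximation), d = (1.960 + 0.842) × √(2/n), which is 1.14 for n = 12 and 1.06 for n = 14.

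**Step 6. Illustration of sensitivity.** Only the 14 per group comes from the plan. Assumed inputs are a control mean of 3 manoeuvres, a true ratio of 0.6, and counts that are Poisson or negative binomial with k = 2. I used a two-sided independent t-test at 0.05, since the groups are different patients, and 200,000 simulated trials per row.

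Observed ratio = true ratio × (marked fraction, device ÷ marked fraction, control).

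| Marked: control / device | Observed ratio | p<0.05, Poisson | p<0.05, neg. binomial |
|---|---|---|---|
| 90% / 90% | 0.6 × 1.00 = 0.60 | 47% | 24% |
| 85% / 90% | 0.6 × 1.059 = 0.635 | 38% | 19% |
| 75% / 90% | 0.6 × 1.20 = 0.72 | 21% | 12% |
| 90% / 85% | 0.6 × 0.944 = 0.567 | 54% | 28% |
| 90% / 75% | 0.6 × 0.833 = 0.50 | 68% | 38% |

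At 75% / 90%, a true ratio of 0.833 would read as 0.833 × 1.20 = 1.00, so a true 17% reduction would disappear.

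With no device effect, suppose behaviour or marking alone lowers the group 1 count by 20%. The chance of p<0.05 then rises from 5% to 12%, 19% or 26% for Poisson control means of 2, 4 or 6. A 30% lower count gives 21%, 38% or 52%.

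**The case against.** A reader might infer that only group 1 providers receive study papers and that control providers carry none. The text says neither. Where the protocol limits something to one arm, as with the survey, it says so, and the 10-minute contact before the case is open to both arms. That objection stands: the asymmetry is a reading of the paragraph's order. The statement that "For both patient groups, the study procedure is the same" adds little on the other side, because it leads into how patients are identified, not how providers are briefed.

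A reader might also infer that group 1 providers are coached on the outcome. This is not supported. The described content is device use and placement, some of which is needed to deliver an unfamiliar mouthpiece that the provider may remove, and the one instruction on recording is shared by both arms.

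The strongest point is the in-room observer. If the observer's count is the primary outcome, differential marking by providers largely ceases to matter. This stands as far as it goes, but the plan does not name the source of the count, and an observer cannot correct a change in how readily the provider intervenes. A matching control sheet would not remove that open-label effect either.

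Finally, the simulated figures rest on assumed marking rates, and even with equal marking the scenario has 47% or 24% power. They cannot be read as an estimate of what this trial would lose.

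**Conclusion.** The point holds in a limited form. Read in context, group 1 providers get a briefing, a question sheet and a protocol to carry, and no matching control material is described. Because the provider is unblinded and the threshold for marking is a matter of judgement, this is an avoidable difference between the arms around the primary count.

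Neither its direction nor its size can be derived from the documents. In the assumed scenarios, a marking gap of 5 to 15 percentage points moves the chance of p<0.05 anywhere from 21% to 68% (Poisson) or 12% to 38% (negative binomial), against 47% and 24% with equal marking. These figures show only that a 28-patient trial is sensitive to such a gap. The conclusion rests on the group 1 reading of the paragraph. If both arms are meant to get the papers, the plan needs only to say so and state what they contain. The change is worth making before the first case, because analysis cannot repair the problem afterwards.

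**What to change.** 1. Give the provider of every case, in both groups, the same scripted briefing and the same one-page sheet. The sheet lists the manoeuvres counted under STUDY ENDPOINTS and the mark-now rule.
2. Limit the group 1 extra to a separate device-handling card with no statement of expected effect. State in the protocol who receives each paper and what it contains.
3. Name the in-room observer's count, already provided for under PROCEDURES INVOLVED, as the source of the primary endpoint, with mark-now entries as a check.

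The cost is one more printed sheet for 14 control cases and a few minutes of those providers' time, within a contact that the protocol already describes without limiting it to an arm. The open-label effect on the decision to intervene remains and should be acknowledged as a limitation.
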